2.2. Study Design

In this open-label, non-comparative, observational, non-interventional, retrospective and multi-center study, post-marketing surveillance data will be collected retrospectively for up to 6 months from the initial administration day of the Xyntha Solofuse prefilled syringe injected into patients who have been administered the Xyntha Solofuse prefilled syringe (as part of routine treatment at the Korean health care center which has certified investigators). If the study subject has not completed the 6-month treatment, relevant data should be collected based on the medical records within the 30 days after the last administration of the drug.

Statistical Analysis Plan for rPMS

2.3. Study Population

2.3.1. Inclusion Criteria

To be eligible to enroll in this study, the study subjects will have to meet all the following inclusion criteria:

- 1) Hemophilia A (congenital factor VIII deficiency) patients who have been administered according to the indication of the product.
 - ① Control and prevention of bleeding episodes and for routine and surgical prophylaxis in patients with hemophilia A (congenital factor VIII deficiency).
 - ② This drug does not contain von Willebrand factor and, therefore, is not indicated in von Willebrand's disease.
- 2) Those who have been administered the Xyntha Solofuse prefilled syringe at least once.

2.3.2. Exclusion Criteria

Patients who satisfy the following criteria are not included in the study according to the local labeling:

- 1) Patients who have a history of hypersensitivity to the Xyntha Solofuse prefilled syringe or the ingredients of this drug.
- 2) Patients who have a history of hypersensitivity to hamster proteins.
- 3) Patients who have bleeding disorders other than hemophilia A.
- 4) Patients who have a history of FVIII inhibitors, or currently have or are suspected of having FVIII inhibitors. In case inhibitor titers quantified in Bethesda Units in the laboratory test results are within the normal laboratory range or at least 0.6 BU/mL. If laboratory tests cannot be performed, the investigator will determine whether or not inhibitors exist based on the clinical assessment results that show a decrease in efficacy of the replacement of FVIII (e.g. bleeding at least once, if the replacement of anti-bleeding agents is needed to be administered, and if frequency or dosage of replacement FVIII therapy needs to be increased).
- 5) Use of immunomodulatory therapy (e.g. intravenous injection of immunoglobulin, use of regular systemic corticosteroids, cyclosporine, and mediators of anti-TNF- α).

2.4. Sample size Considerations

The calculation of sample size is not applicable for this study. At least 600 study subjects will be enrolled in this study to meet the MFDS requirements. Although 600 is the assigned number of study subjects, the number of cases will be adjusted considering the actual number of enrolled subjects after the study start day.

Statistical Analysis Plan for rPMS

3. Analysis Populations

3.1. Safety Analysis Set

Safety analysis set will include study subjects who have been administered to the Xyntha Solofuse prefilled syringe at least once, and have been evaluated for a safety parameter at least once in relation to the administration.

The following cases will be excluded from the safety analysis set in the following order.

- 1) Subjects who have not been administered for Xyntha solofuse prefilled syringe.
- 2) Subjects who have not met the inclusion/exclusion criteria.
- 3) Subjects who have experienced off-label use against Xyntha solofuse prefilled syringe local product document.

3.2. Efficacy Analysis Set

Efficacy analysis set will include study subjects adequate for efficacy evaluation at least once among the safety analysis set.

The following cases will be excluded from the efficacy analysis set in the following order.

- 1) Subjects who are excluded from the safety analysis set.
- 2) Subjects without efficacy assessment endpoint.
 - On-demand treatment: Responses to the injection of the Xyntha Solofuse prefilled syringe
 - Prophylactic therapy: Subjects who have experienced bleeding (overall, spontaneous)

3.3. Special Patient Population

Special patient populations will includes pediatric subjects (age<19), elderly subjects (age≥65), patients with renal or hepatic disorders, pregnant women, respectively.

3.4. Population excluded from Safety Analysis

Population excluded from safety analysis set will be accounted for as part of the subject accounting in the report. However, subjects who have not been administered for Xyntha solofuse prefilled syringe will be excluded from this analysis set. Any adverse events reported for subjects excluded from the Safety Analysis Set will also be described.

The following cases will be included in this analysis set.

- 1) Subjects who have not met the inclusion/exclusion criteria.
- 2) Subjects who have experienced off-label use against Xyntha solofuse prefilled syringe local product document.

Statistical Analysis Plan for rPMS

3.5. Subgroups Patient Population

Subgroups patients populations will be classified into the patients who have been treated previously and patients who have not been treated, and status of treatment experience previously define previous exposure to plasma-derived factor VIII.

4. Study Endpoints

4.1. Demographics and Baseline Characteristics

- 1) State (age and sex) of the study subjects

4.2. History of hemophilia A

- 1) Duration of the disease
- 2) Genetic mutation of factor VIII
- 3) Previous exposure to plasma-derived factor VIII
- 4) Previous used factor VIII therapy
- 5) Personal history of allergic reactions to factor VIII products (within 12 months)
- 6) Family history of hemophilia A
- 7) Family history of factor VIII inhibitors
- 8) Family history of allergic reactions to factor VIII products (within 12 months)
- 9) Severity

4.3. Medical History

- 1) Renal/hepatic disorder
- 2) Past/present disease status
- 3) Past/present disease (Status (Yes/No), past/present disease classified by 092 version of WHO-ART(World Health Organization-Adverse Reaction Terminology))

4.4. Concomitant Treatments/Therapy

- 1) Concomitant medication (Status (Yes/No), Level1, Level2 of concomitant medication classified by latest version of KIMS code)
- 2) Concomitant therapy (Status (Yes/No), Level1, Level2 of concomitant therapy classified by latest version of KIMS code)

4.5. Administrative Status for Medicinal Products

- 1) Single infusion dosage.
- 2) Total infusion dosage.

Statistical Analysis Plan for rPMS

3) Duration of administration

4.6. Safety Endpoints

- 1) The incidence and number with 95% confidence Interval for all adverse events/adverse drug reactions investigated within 6 months from initial administration after at least 1 dose of Xyntha solofuse prefilled syringe (If the study subject has not completed the 6-month treatment, relevant data should be collected based on the medical records within the 30 days after the last administration of the drug)

- ① Severity
- ② Action taken
- ③ Seriousness
- ④ Outcome
- ⑤ Causality assessment

2) Laboratory Test

- ① Blood test(Hemoglobin, Hematocrit, RBC, WBC, Platelet Count, ESR, CRP)
- ② Biochemical test(AST(SGOT), ALT(SGPT), ALP, BUN, Creatinine, Factor VIII Inhibition Factor Hemoglobin)
- ③ Urine examination(Protein/Albumin, Glucose/Sugar, Hemoglobin/Blood)

4.7. Efficacy Endpoints

1) On-demand treatment

- ① Responses to all the injection of the Xyntha Solofuse prefilled syringe used to treat bleeding (4 point scale: excellent, good, moderate, and no response)
 - Excellent: Definite pain relief and/or improvement in signs of bleeding starting within 8 hours after an infusion, with no additional infusion administered. Point = 1.
 - Good: Definite pain relief and/or improvement in signs of bleeding starting within 8 hours after an infusion, with at least one additional infusion administered for complete resolution of the bleeding episode. Or, definite pain relief and/or improvement in signs of bleeding starting after 8 hours after an infusion, with no additional infusion administered. Point = 2.
 - Moderate: Probable or slight improvement starting after 8 hours following the infusion, with at least one additional infusion administered for complete resolution of the bleeding episode. Point = 3.
 - No Response: No improvement at all between infusions or during the 24 hour interval following an infusion, or condition worsens. Point = 4.
- ② Number of observations of less than expected therapeutic effect (LETE)
 - If the response to treatment of Xyntha solofuse prefilled syringe assess "no

Statistical Analysis Plan for rPMS

response" after each infusion of 2 consecutive infusions within 24 hours after on-demand treatment, LETE will be calculated once, if it assess "no response" after each infusion of 3 consecutive infusion within 24 hour, LETE will be calculated twice

- ③ In case of bleeding: The number of infusions of Xyntha Solofuse prefilled syringes used to treat each new bleeding episode will be rated.
 - ④ Mean infusion dosage
- 2) Prophylactic Therapy
- ① Percentage of the study subjects who have experienced bleeding (overall, spontaneous)
 - ② Annualized Bleeding Rates (ABRs)
 - ③ Number of observations of less than expected therapeutic effect (LETE)
 - If atypical bleeding occur within 48 hours after administration of the Xyntha Solofuse Prefilled Syringe by dosage for the prevention of bleeding (spontaneous/at traumatic), LETE will be calculated once.
 - ④ Mean infusion dosage
 - ⑤ Total factor consumption (Total infusion dosage)

5. General Consideration

5.1. Analysis Principles

Statistical analysis will be conducted after database is locked and performed using SAS software version 9.4 according to this statistical analysis plan. If statistical analysis methods are changed, it will be described in the final study report.

Continuous variables will be summarized by the descriptive statistics (n, mean, median, SD (standard deviation), minimum, and maximum). Categorical variables will be presented in the frequency distribution table (n, %).

In case of statistical hypothesis testing, two-sided test will be conducted under 5% significance level and the p-value of each test result will be presented in the summary table.

6. Statistical Analyses

6.1. Demographic and Baseline Characteristics (frequency and percentage)

- 1) Sex (Male, Female)
- 2) Age (< 30 years, 30 ~ 39 years, 40 ~ 49 years, 50 ~ 59 years, ≥ 60 years)

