7.2.4. Administration and Dosage

This drug should be initiated under the supervision of a physician experienced in the treatment of hemophilia A.

This drug is appropriate for use in adults and children of all ages, including newborns.

Formula

$$\begin{array}{rclclclcl} \text{Required} & = & \text{body} & \times & \text{desired factor VIII rise} & \times & 0.5 \\ \text{units} & & \text{weight} & & \text{(IU/dL or normal \%)} & & \text{(IU/kg per IU/dL)} \\ & & \text{(kg)} & & & & \end{array}$$

Precise monitoring of the replacement therapy by means of plasma factor VIII activity assay should be considered, particularly for surgical intervention.

Dosing for Bleeding and Surgery

In the cases of the following hemorrhagic events, consideration should be given to maintaining the factor VIII activity at or above the plasma levels (in % of normal or in IU/dL) for the indicated period, as outline in the following table.

<Maintenance of Factor VIII Activity for Various Hemorrhagic Events>

Degree of Hemorrhage/ Type of surgical procedure	Factor VIII Level Required (% or IU/dl)	Frequency of Doses (hours) /Duration of Therapy (days)
Bleeding Early hemathrosis, minor muscle or oral bleeds	20-40	Repeat every 12 to 24 hours as necessary until resolved. At least 1 day, depending upon the severity of the bleeding episode.
Bleeding into muscles. Bleeding into the oral cavity. Mild head trauma.	30-60	Repeat infusion every 12 to 24 hours for 3-4 days or until adequate local hemostasis is achieved.
Gastrointestinal bleeding. Intracranial, intra-abdominal or intrathoracic bleeding. Fractures.	60-100	Repeat infusion every 8 to 24 hours until bleeding is resolved.
Surgery Minor operation (including tooth extraction)	30-60	Repeat infusion every 12 to 24 hours for 3-4 days or until adequate local hemostasis is achieved. For tooth extraction, a single infusion plus oral antifibrionlytic therapy within 1 hour may be sufficient.
Major operation	60-100	Repeat infusion every 8 to 24 hours until threat is resolved, or in the case of surgery, until adequate local hemostasis and wound healing are achieved. Then continue therapy for at least another 7 days to maintain the factor VIII activity at 30 to 60% (IU/dl)

Dosage for Prophylaxis

This drug has been administrated prophylactically in a pivotal clinical trial in adolescent and adult previously treated patients at a dose of 30 ± 5 IU/kg given 3 times weekly.

Administration

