 - Not related to this medicinal product:
 - IV. Unlikely
- 3) Occurrence status of adverse event by demographics and baseline characteristics
- Occurrence status of adverse events will be presented in frequency and percentage and incidence proportion with 95% confidence interval based on categorical variables of demography and baseline characteristics of the patients (sex, age group, past/present disease status, renal/hepatic disorder status). To identify statistically significant difference in occurrence of adverse events among demography and baseline characteristics, Chi-square test or Fisher's exact test will be performed.
- 4) Occurrence status of adverse event by concomitant treatment/therapy
- Occurrence of adverse events will be presented in frequency and percentage and incidence proportion of adverse events with 95% confidence interval by concomitant treatment status and concomitant therapy status. To identify statistically significant difference in occurrence of adverse events among concomitant treatment status, concomitant therapy status, Chi-square test or Fisher's exact test will be performed.
- 5) Analysis of factors that affect safety
- Logistic regression analysis will be performed and an odds ratio with 95% confidence interval will be presented to identify the factors that affect occurrence of adverse events in demography and baseline characteristics (sex, age group, past/present disease status, renal/hepatic disorder status), or concomitant treatment status, concomitant therapy status, etc.

Statistical Analysis Plan for rPMS

- 6) Test of difference for laboratory data before and after administration.
Laboratory data before and after administration will be presented by descriptive statistics and test of difference for laboratory data before and after administration will be performed by using paired t-test (or Wilcoxon signed-rank test). This analysis will be performed if possible.
- 7) Distribution for special patient populations (children (age<19), elderly (age≥65), renal disorder, hepatic disorder, pregnant woman) will be presented. Also, adverse events and adverse drug reactions collected by these groups will be presented in incidence proportion and number events of it for each SOC and PT.

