4) Overall efficacy assessment will be classified as effective/not-effective as follows, presented in frequency and percentage of it.

- ① On-demand treatment

- [Effective]: Subjects with whom the best responses 'Excellent' or 'Good' or 'Moderate'.
- [Not-effective]: Subjects with whom the best responses 'No response'.

- ② Prophylactic Therapy

- [Effective]: Subjects who haven't experienced any atypical bleeding within 48 hours after administration of the Xyntha Solofuse Prefilled Syringe.
- [Not-effective]: Subjects who have experienced at least once atypical bleeding within 48 hours after administration of the Xyntha Solofuse Prefilled Syringe.

5) Efficacy assessment by demographics and baseline characteristics

Classified overall assessment (effective/not-effective) will be presented in frequency and percentage based on categorical variables of demography and baseline characteristics (sex, age group, past/present disease status, renal/hepatic disorder status). To identify statistically significant difference of frequency distribution of classified overall assessment (effective/not-effective) among demography and baseline characteristics, Chi-square test or Fisher's exact

Statistical Analysis Plan for rPMS

test will be performed.

- 6) Efficacy assessment by concomitant treatment (Concomitant Treatments/Therapy status)
Classified overall assessment (effective/not-effective) will be presented in frequency and percentage for concomitant treatment status (Concomitant Treatments/Therapy status). To identify statistically significant difference of frequency distribution of classified overall assessment (effective/not-effective) among concomitant treatment status, concomitant therapy status, Chi-square test or Fisher's exact test will be performed.
- 7) Analysis of factors that affect efficacy
Logistic regression analysis of multivariate analysis will be performed and presented an odds ratio with 95% confidence interval to identify the factors that affect classified overall assessment (effective/not-effective) in demography and baseline characteristics of the patients (sex, age group, past/present disease status, renal/hepatic disorder status), or concomitant treatment status, concomitant therapy status, etc.

7. Reporting Principles

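### The SAP's age bands have no boundary at its own <19 and ≥65 cut-offs, so no test, model term or efficacy output isolates children or the elderly

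*SAP*

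**What the plan says.** SAP 6.1 lists the age categories as "Age (< 30 years, 30 ~ 39 years, 40 ~ 49 years, 50 ~ 59 years, ≥ 60 years", for reporting by frequency and percentage. No other age grouping is given for baseline characteristics, and no continuous summary of age is listed there.

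SAP 3.3 names "pediatric subjects (age<19), elderly subjects (age≥65" among the special patient populations. SAP 6.6(7) uses the same cut-offs: "Distribution for special patient populations (children (age<19), elderly (age≥65), renal disorder, hepatic disorder, pregnant woman) will be presented". It adds incidence proportions and event counts of adverse events and adverse drug reactions by system organ class and preferred term.

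Age group enters four planned analyses:

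- **6.6(3):** chi-square or Fisher tests on adverse events, over "sex, age group, past/present disease status, renal/hepatic disorder status".
- **6.6(5):** the safety model. "Logistic regression analysis will be performed and an odds ratio with 95% confidence interval will be presented to identify the factors" that affect adverse event occurrence.
- **6.7(5):** chi-square or Fisher tests on the effective/not-effective classification, over the same factors.
- **6.7(7):** the efficacy model. "Logistic regression analysis of multivariate analysis will be performed and presented an odds ratio with 95% confidence interval".

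Protocol 7.2.4 states: "This drug is appropriate for use in adults and children of all ages, including newborns". The inclusion criteria (protocol 7.2.1, SAP 2.3.1) set no age limit.

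**The concern.** The SAP holds two age schemes that do not nest. The under-30 band may contain anyone from a newborn to a 29-year-old, and the other four bands divide adults aged 30 and over. The groups that the SAP itself singles out, children and elderly, therefore cannot be rebuilt by combining bands. They have no test, no odds ratio and no efficacy table.

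The product is used from birth for a congenital disease, so whether children differ from adults is an obvious question for the analyses of factors affecting safety and efficacy. As written, those analyses compare a mixture of children and young adults with older adults. They also spend four age parameters doing so, in a study that protocol section 5 expects to yield at least 86 analysable subjects. Because the schemes do not nest, the age-group tables also cannot be cross-checked against the special-population tables.

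**Working it through.** The documents state no effect size, power or sample-size calculation, so there is no planned figure to reproduce.

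**Step 1: do the cut-offs fall on boundaries?** The 6.1 boundaries are 30, 40, 50 and 60. The 3.3 cut-offs are 19 and 65. Age 19 lies inside <30 and 65 lies inside ≥60, so neither special population is a union of bands.

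**Step 2: what output exists at 19 and 65?**

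| Output | <19 and ≥65 |
|---|---|
| Adverse event incidence by SOC and PT | Yes, 6.6(7), descriptive; no stated comparator, test or confidence interval |
| Adverse event test, 6.6(3) | Not isolated |
| Adverse event model, 6.6(5) | Not isolated |
| Efficacy tables, 6.7(1) to 6.7(4) | None |
| Efficacy test and model, 6.7(5) and 6.7(7) | Not isolated |

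By contrast, 6.6(3) and 6.6(4) do specify 95% confidence intervals.

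**Step 3: how much dilution? (illustration)** From the documents: 86 subjects (protocol section 5) and two-sided 5% tests (SAP 5.1). Assumed, because the documents give no age distribution or event rates: adverse event risk 10% in all adults and 30% or 40% in children, with these numbers by age:

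| Share <19 | <19 | 19–29 | 30–39 | 40–49 | 50–59 | ≥60 |
|---|---|---|---|---|---|---|
| 15% | 13 | 17 | 22 | 17 | 10 | 7 |
| 30% | 26 | 17 | 17 | 13 | 9 | 4 |
| 45% | 39 | 13 | 13 | 10 | 7 | 4 |

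Risk in the <30 band = (children × child risk + those aged 19–29 × 10%) / band size. With child risk 30%:

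- 15%: (13 × 0.30 + 17 × 0.10) / 30 = 5.6 / 30 = 18.7%, which is 8.7 points above other adults; odds ratio 2.07.
- 30%: (7.8 + 1.7) / 43 = 22.1%, 12.1 points; odds ratio 2.55.
- 45%: (11.7 + 1.3) / 52 = 25.0%, 15.0 points; odds ratio 3.00.

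The true contrast is 20 points, with odds ratio (0.30/0.70) / (0.10/0.90) = 3.86.

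**Step 4: power of the tests.** Pearson chi-square power by simulation, for 15%, 30% and 45% children in that order. In the three-class row the oldest band stands in for ≥65.

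| Age grouping (df) | Child risk 30% | Child risk 40% |
|---|---|---|
| Five bands, as planned (4) | 0.07, 0.09, 0.09 | 0.14, 0.25, 0.31 |
| <19, 19–64, ≥65 (2) | 0.40, 0.53, 0.52 | 0.66 to 0.85 |
| <19 vs ≥19 (1) | 0.50, 0.64, 0.67 | 0.75, 0.89, 0.93 |

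For 30% vs 10%, Fisher's exact test on the single split gives 0.43, 0.56 and 0.60. Under modestly different assumed age shares, the five-band figure ranges over about 0.06–0.11 and the three-class figure over about 0.40–0.55.

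**The case against.** **Stronger readings that the documents do not support.** A reader might infer that the plan cannot show a paediatric difference at all. That goes too far. SAP 6.6(7) reports adverse events in children and elderly, and overall adverse event figures appear under 6.6(1), so a marked excess could be seen descriptively. A reader might also infer that a child/adult contrast vanishes in the under-30 band. It is diluted. If 60% of the band were children at 20% risk and 40% were young adults at 5%, the band would show 0.6 × 20% + 0.4 × 5% = 14%, still 2.8 times the 5% in other adults if they share that rate. Nor do the documents show that older adults will be few, since they give no age distribution.

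**The case for leaving the bands alone.** Decade bands and special-population reporting serve different purposes, and nothing in the documents requires them to nest. The age tests are exploratory in a non-comparative, retrospective surveillance study whose primary objective is to detect factor VIII inhibitor. The protocol permits further sub-analysis if the data are adequate, and the factor lists for the SAP models are open-ended. A ≥65 class may itself be sparse, and a single 19–64 class hides any gradient among adults. The SAP also does not say expressly that age group means the 6.1 bands.

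**What stands.** The low stakes and the possible sparsity of ≥65 stand, and they limit both the weight of the point and the form of the fix. The permissive wording leaves room for a contrast at 19 but does not prespecify one. As to what age group means, 6.1 is the only candidate for a baseline age grouping. If another was intended, the SAP needs to state it.

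**Conclusion.** The point holds as a cheap improvement to exploratory analyses. It does not threaten the primary objective. That 19 and 65 are not band boundaries, and that section 6.7 has no efficacy output for either group, follows from the text with no assumption beyond reading age group as the 6.1 bands.

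The size does rest on assumptions: the age shares, a 10% adult risk common to all adult ages, and a 30% child risk. Under these, five bands give power of about 0.06–0.11, three classes about 0.40–0.55 and a single split at 19 about 0.5–0.67. The ordering is the same at 40% child risk. Even the best of these is modest at about 86 subjects, so a non-significant age result would not show that children and adults are alike. The estimate with its interval is the more useful output.

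**What to change.** In SAP 6.1, define the age classes for 6.6(3), 6.6(5), 6.7(5) and 6.7(7) as <19, 19–64 and ≥65, and state that age group in those items means these classes. If ≥65 is too sparse, merge it with 19–64 in the tests and models. Then:

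- report the <19 versus ≥19 difference or odds ratio with a 95% confidence interval, for adverse events and for the overall efficacy classification;
- add <19 and ≥65 rows to the efficacy tables in 6.7;
- keep the adult decades as a descriptive row in the demographic table.

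Age is already collected (protocol 7.2.5.1), so the cost is a recode and a few lines of SAP text, with no new data. The downside is that decade detail among adults leaves the exploratory tests and models.
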